Association between the Irrigation-Agitation Techniques and Periapical Healing of Large Periapical Lesions: A Randomized Controlled Trial

Clinical Trial Number: NCT06204887

Date: 16.05.2024

STUDY PROTOCOL

Local ethics committee approval was obtained from the Ethical Review Committee of the Research Foundation at the Medical Faculty of Recep Tayyip Erdogan University (No: 2023/35) and the study protocol was registered at ClinicalTrials.gov (NCT06204887).

Sample size calculation

The G Power 3.0.10 (University Kiel, Germany) program was used to calculate the effect size. The effect size was calculated based on chi-square analysis data between the control group and the laser group in the Verma, Yadav study [26]. An effect size of 0.51 Cohen d value was found to be sufficient for significance. With a type 1 error of 0.05, it was determined that at least 56 subjects were required for a total of 4 groups, 14 in each study group, with 95% power.

Patient Recruitment and Randomization

Patients were informed about the procedure, and written informed consent was obtained before the commencement of treatment. The study included mandibular single-rooted teeth that were diagnosed with asymptomatic apical periodontitis and had a periapical index (PAI) score of 3 or higher. A total of 97 patients aged 18-65 were evaluated radiographically and clinically for conformity with the inclusion and exclusion criteria. Patients with systemic diseases (diabetes, hypertension, chronic liver disease, coagulation disorders), bone metabolism disease and/or patients using drugs that affect bone metabolism (such as steroids and bisphosphonates) were excluded from the study. Immunosuppressed patients, patients with a history of radiotherapy, pregnant patients, patients with teeth with a mobility of 2 or more (Miller's mobility index), patients with teeth with a periodontal pocket depth of 5 mm or more, patients with generalized asymptomatic apical periodontitis, patients with teeth with internal and external resorption, and patients with teeth with vertical and horizontal root fractures were not included.

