After applying the eligibility criteria, 70 patients were randomly divided into four groups using software (www.random.org) by a blinded researcher who was not otherwise involved in the study according to a standardized procedure. The numbers were placed in dark envelopes and concealed. The envelopes were only opened when the irrigation solution was to be activated. The patients were informed about the study without specifying the group to which they were assigned. All procedures were performed by a single operator with five years of experience ([name]).

CBCT imaging (Planmeca Romexis, Helsinki, Finland) was requested for patients who met the study criteria before the procedure to obtain information about periapical lesion size, proximity to anatomical landmarks, and anatomical variations of the tooth. CBCT images were acquired with a field of view (FOV) of 5×5 cm using ENDO mode, an 85 µm voxel size, 6.3 mA, 90 kV, and 8.7 s.

Clinical procedures

A CONSORT flow diagram outlining the treatment methodology is presented in Figure 1. After the administration of local anesthesia and the placement of a rubber dam, the access cavity was opened with a sterile diamond round bur under water cooling. Each canal was rinsed with 2 mL of sodium hypochlorite and explored with a size 08 K-file (FKG Dentaire, La Chaux-de-Fonds, Switzerland). The working length was determined using an electronic apex locator, Root ZX mini (J. Morita Co., Tokyo, Japan), to be 0.5 mm shorter than a 0.0 reading. The length was confirmed radiographically. After that, progressively larger K-files were passively introduced into the canal until the operator felt the first one to bind at the WL and the next larger one not to reach that position [27]. The first instrument used to bind the canal was recorded for each canal. The crown-down technique was applied with ProTaper Next rotary files (Dentsply Maillefer, Ballaigues, Switzerland) using a torque-controlled endodontic motor (SybronEndo, Glendora, CA, USA) at 300 rpm/2-5.2 Ncm rotation mode according to the manufacturer's instructions. The final instrumentation file was set to 3 sizes larger than the first file used[28]. Between each instrument change, the root canal was irrigated with 5 mL of 2.5% NaOCl (Microvem AF, Istanbul, Turkey) for 1 min. After canal preparation was completed, the final irrigation procedure was carried out with the corresponding irrigation method in each group.

[figure not shown]

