The preoperative and 1-year postoperative CBCT images of the patients were measured following the same steps in the ITK-SNAP program. We used the same techniques used by Schloss et al[15]. First, the captured CBCT images were exported in DICOM file format from the Planmeca Romexis software. The exported images were then opened with ITK-SNAP software. Using the highest resolution allowed by the captured CBCT images (0.09 mm), the slice thickness and slice interval were set to 0.09 mm. The ITK-SNAP program includes a semiautomatic segmentation feature, which was utilized. In this feature, automated spherical fillers, or bubbles, as referred to in the program, were placed according to the grayscale of the lesion. Repeated runs were performed until the entire area of the lesion was filled, with the bubbles placed in the lesion area. After the internal area of the lesion was completely filled, the images were evaluated from axial, sagittal, and coronal sections to correct any possible overfilling or underfilling situations due to artifacts from canal filling materials using a manual marker. The volume of the painted area obtained was calculated in mm³ using the program's feature. The evaluation of the tomography images obtained before and after treatment was conducted at one-month intervals. The images were provided to the evaluators in a randomized manner.

The volume data were compared with the preoperative CBCT measurements for each patient. The volume changes were measured, and the long-term outcomes of the procedures were compared.

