Association between the Irrigation-Agitation Techniques and Periapical Healing of Large Periapical Lesions: A Randomized Controlled Trial

Clinical Trial Number: NCT06204887

Date: 16.05.2024

Statistical analysis

Analyses were carried out in the IBM SPSS 25 program. As the first step of the statistical analysis, the normality of the data was checked with the Shapiro–Wilk test. When normality was ensured, the Wilcoxon signed rank test was applied to examine the difference between the means of two dependent groups. ANOVA was used to examine the difference between the means of three or more independent groups. In cases where the data were not normally distributed, the Kruskal–Wallis test was performed. The post hoc Bonferroni correction was used to determine the group or groups that were significantly different.

Pearson's chi-square test was applied to examine the relationships between study groups and sex. The Kruskal–Wallis test was applied to examine the differences between the average ages of the participants in the study groups. Spearman correlations were used to control for the relationships between age and lesion volume measurements obtained at different times and from different study groups. To compare lesion volume measurements according to study group at different measurement times, ANOVA and the Kruskal–Wallis test were applied. Bonferroni correction were performed to compare the groups. Wilcoxon signed rank tests were used to compare lesion volume measurements according to different measurement times in the study groups.

For comparisons of lesion volume measurements at different measurement times in the study groups, assumptions were checked, and Wilcoxon signed-rank tests were used. Analyses were performed with the IBM SPSS 25 (SPSS Inc., Chicago, IL) program. The Pearson chi-square test was used to examine the relationships between study groups and sex. The Spearman correlation test was used to assess the relationships between lesion volume measurements obtained at different times and study group and age.

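### The named between-arm tests of lesion volume leave out baseline volume, which is measured in every patient; baseline-adjusted ANCOVA would be more precise at almost no cost

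*SAP*

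**What the plan says.** The SAP (Statistical analysis) gives one between-arm method for the volume outcome: "To compare lesion volume measurements according to study group at different measurement times, ANOVA and the Kruskal–Wallis test were applied". Bonferroni correction follows for pairwise comparisons. The before/after comparison is a Wilcoxon signed-rank test within each arm. Neither document names an ANCOVA, a regression, a rank-based ANCOVA or a stratified test.

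The Protocol (Healing evaluation) has the pre-operative and 1-year CBCT volumes measured by the same steps. It adds: "The volume data were compared with the preoperative CBCT measurements for each patient". And: "The volume changes were measured, and the long-term outcomes of the procedures were compared". It does not say which test compares the arms on change.

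Age appears in three SAP sentences. The first is "The Kruskal–Wallis test was applied to examine the differences between the average ages of the participants in the study groups". The second is "Spearman correlations were used to control for the relationships between age and lesion volume measurements obtained at different times and from different study groups". The third, at the end of the section, describes the same correlations differently: "The Spearman correlation test was used to assess the relationships between lesion volume measurements obtained at different times and study group and age".

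On size, the Protocol (Sample size calculation) states that "at least 56 subjects were required for a total of 4 groups, 14 in each study group", and under Patient Recruitment and Randomization that "70 patients were randomly divided into four groups".

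**The concern.** Pre-treatment lesion volume is the same quantity as the outcome, measured by the same method a year earlier, so it is the natural candidate to explain variation in 12-month volume. A separate ANOVA or Kruskal–Wallis test at 12 months leaves that variation in the error term. The within-arm Wilcoxon tests do link the two times, but they do not compare arms. A test of volume between arms at baseline, like the test of age between arms, adjusts nothing at 12 months.

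At stake are wider intervals and lower power than the collected data allow, in arms planned at 14. A lesser issue is that a reader of the first Spearman sentence could believe the treatment comparison had been controlled for age.

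**Working it through.** **The plan's own figure.** The plan gives no correlation, SD or expected interval width, so it has no precision figure to reproduce. Its sample size of 56 serves here only as N. That figure does not follow from the stated description: with 0.51 taken as w, a chi-square test at 95% power needs 50, 60 or 67 patients (1, 2 or 3 df), and a four-group ANOVA with f = 0.51 needs 72. This is a separate matter, and the precision result does not depend on it.

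**Inputs.** N = 56 (4 × 14) and N = 70 (randomised, before any loss), both from the Protocol. Alpha is 0.05, also from the Protocol. The correlation r between baseline and 12-month volume within arms is assumed at 0.1, 0.3, 0.5 and 0.7. A normal outcome is assumed.

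**Step 1: SE with one covariate.** Relative to the unadjusted 12-month comparison, and including the one df paid and chance baseline imbalance:

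SE ratio = √[(1 − r²)(1 + 1/(N − 6))]

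For N = 56 the second factor is 1 + 1/50 = 1.02. At r = 0.5: √(0.75 × 1.02) = √0.765 = 0.875.

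| r | N = 56 | N = 70 |
|---|---|---|
| 0.1 | 1.005 | 1.003 |
| 0.3 | 0.963 | 0.961 |
| 0.5 | 0.875 | 0.873 |
| 0.7 | 0.721 | 0.720 |

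Break-even at N = 56 is where 1 − r² = 1/1.02, that is r = 0.14.

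**Step 2: would comparing change do the same?** With equal SDs at both times, the SE ratio for change is √[2(1 − r)]: 1.183, 1.000 and 0.775 at r = 0.3, 0.5 and 0.7. ANCOVA gives 0.963, 0.875 and 0.721. If the baseline SD is k times the 12-month SD, the variance ratio for change is 1 + k² − 2rk, which is below 1 only when r > k/2. Change therefore helps only when r is high relative to k.

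**Step 3: power of the four-arm F test.** The Protocol's effect size is 0.51, labelled Cohen d, and it can be read two ways: as f = 0.51, or as a largest gap between arms of d = 0.51, for which f is at most d/2 = 0.255. Noncentrality is N f²/(1 − r²), with one df lost for the covariate. This ignores chance baseline imbalance, so the adjusted figures are slightly generous.

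| N, f | Unadjusted | r = 0.3 | r = 0.5 | r = 0.7 |
|---|---|---|---|---|
| 56, 0.51 | 88.4% | 91.3% | 95.9% | 99.5% |
| 70, 0.51 | 95.0% | 96.7% | 98.8% | 99.9% |
| 56, 0.255 | 30.7% | 33.4% | 40.0% | 56.3% |
| 70, 0.255 | 38.3% | 41.7% | 49.7% | 67.8% |

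**Step 4: does age matter?** Adding age to baseline volume at r = 0.5 (N = 56) moves the SE ratio from 0.875 to √[0.75 × (1 + 2/49)] = 0.884 if age is unrelated to the outcome. If age is independent of baseline volume and correlates 0.2 with the outcome, the ratio is √[(1 − 0.25 − 0.04)(1 + 2/49)] = 0.860. Most of the gain comes from baseline volume.

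**The case against.** The strongest reply is that nothing here is an error. The unadjusted test is valid after randomisation, ANCOVA is a matter of good practice, and the whole gain rests on a correlation that the documents do not give. All of that stands. At r = 0.3 the SE gain is about 4%. With f = 0.51 and all 70 patients, power is already about 95% and rises by only 2 to 5 points. With f = 0.255 the trial stays short of power at r = 0.3 or 0.5 with or without the covariate. The calculations also assume normality, while the SAP keeps Kruskal–Wallis for non-normal data; the gain was not worked out for a skewed outcome or a rank test.

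The next reply is that the Protocol measured volume changes, so baseline may already have entered the comparison. This stands in part. A reader might infer that baseline was ignored altogether, but the documents do not support that; they leave open how change was compared between arms. With equal SDs and r = 0.7, change recovers most of the gain (0.775 against 0.721). At r = 0.5 it recovers none, and at r = 0.3 it is worse than no adjustment.

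A reader might also infer that the SAP promised an age-adjusted treatment comparison and did not deliver it. The text is too thin for that. The closing sentence of the SAP says the same correlations assess relationships, so the earlier phrase is most plausibly loose wording, and no sentence claims an adjusted arm comparison.

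**Conclusion.** The point holds as a cheap improvement in precision. No between-arm test named in the SAP uses baseline volume, although it is available for every patient. Adjusting for it alone would cut the SE of an arm difference by about 4%, 13% or 28% at an assumed r of 0.3, 0.5 or 0.7 (N = 56, normal outcome), and would cost about 0.5% at r = 0.1. The direction is secure for any r above about 0.14; the size is not known from the documents. Omitting baseline or age does not bias a randomised comparison. The age wording is a minor inconsistency between two SAP sentences and affects no treatment result.

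**What to change.** 1. Compare 12-month lesion volume between arms by ANCOVA with arm and baseline volume, on one scale fixed in advance. One option is log volume at both times, with a small stated constant added so that fully healed lesions can be included. Do not choose the scale from the outcome data.
2. Report adjusted arm differences with 95% CIs and Bonferroni-corrected pairwise contrasts. Age may be added, but the gain does not need it.
3. If outcomes had been seen before the model was fixed, label it post hoc and show it beside the unadjusted result. The SAP is written in the past tense with 70 patients already randomised, so this may well apply.
4. State whether the arms were also compared on volume change, and by which test.
5. For the age–volume Spearman correlations, replace *to control for* with *to describe*, in line with the closing sentence of the SAP.

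The cost is one degree of freedom and a few lines of SAP text. No new visit, scan or measurement is needed.

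### No between-arm comparison of 12-month lesion volume is named that uses preoperative volume as a covariate or in a change score; the planned comparison is valid but may give away power

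*SAP*

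**What the plan says.** The SAP (Statistical analysis) names three kinds of analysis of lesion volume.

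- Between arms: "To compare lesion volume measurements according to study group at different measurement times, ANOVA and the Kruskal–Wallis test were applied", with Bonferroni correction for the comparisons between groups.
- Over time: "Wilcoxon signed rank tests were used to compare lesion volume measurements according to different measurement times in the study groups".
- Against age: "Spearman correlations were used to control for the relationships between age and lesion volume measurements obtained at different times and from different study groups".

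It also has a general rule, "ANOVA was used to examine the difference between the means of three or more independent groups", with Kruskal–Wallis as the fallback when normality fails. That rule names no outcome variable.

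The protocol (Healing evaluation: lesion area and volume calculation) says of the measurements: "The preoperative and 1-year postoperative CBCT images of the patients were measured following the same steps in the ITK-SNAP program". It continues: "The volume data were compared with the preoperative CBCT measurements for each patient", and then "The volume changes were measured, and the long-term outcomes of the procedures were compared". It names no test for comparing those changes between arms.

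**The concern.** The trial measures preoperative volume in each patient, with the same software and steps as the 12-month volume, and the protocol describes the result as a change for each patient. The SAP does not carry this into the comparison between techniques. Its between-arm tests take each time point separately, its pre/post tests stay inside each arm, and its only language of control concerns age.

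Power is at stake. The arms are small: 14 each in the sample size calculation. Eligibility sets only a floor on severity (PAI 3 or higher), and no stratification by lesion size is described, so preoperative volume can vary widely and differ between arms by chance. If it predicts the 12-month volume, the planned test leaves in noise that a measurement already taken could remove.

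**Working it through.** **Inputs.** From the protocol: four arms, 14 per arm, alpha 0.05, 70 randomised ("70 patients were randomly divided into four groups using software"). Not in the documents, and so assumed: rho (0 to 0.7), the shift in one arm (0.9 SD, with 0.51 SD as an alternative), and the share of lesions at 0 mm³. For the 70 patients, a 17/17/18/18 split and no loss to follow-up are also assumed.

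**The plan's own figure.** The total of 56 is not reproduced by the obvious readings of the stated 0.51 at 95% power. A two-sample t test with d = 0.51 needs 101 per arm, and a four-group ANOVA with f = 0.51 needs 71 in total. That is a separate matter; only the arm size of 14 is used here.

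**1. Validity.** Randomisation gives the arms equal expected preoperative volume. The difference between arms in mean change therefore equals the difference in mean 12-month volume, and ANOVA at 12 months targets it without bias. Kruskal–Wallis, a rank test, does not target a mean change, but it is a valid test of no difference. Simulated rejection under the null, for rho 0 to 0.7 and 0 to 49% zeros, was 0.044–0.053 for ANOVA, 0.044–0.050 for Kruskal–Wallis and 0.048–0.054 for Quade.

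**2. Parametric case.** With one of four arms shifted by δ SD, the noncentrality is λ = n × δ² × (1 − 1/4) = 14 × 0.81 × 0.75 = 8.505. ANOVA (3 and 52 df) then has 64.7% power. Adjustment multiplies residual variance by 1 − rho², so λ becomes 8.505/(1 − rho²), with 51 residual df:

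- rho 0: λ 8.51, power 64.7%
- rho 0.3: 8.505/0.91 = 9.35, power 69.2%
- rho 0.5: 8.505/0.75 = 11.34, power 78.3%
- rho 0.7: 8.505/0.51 = 16.68, power 92.5%

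Simulation gives 63.8, 68.4, 77.6 and 92.3% for ANCOVA, within about 1 point.

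**3. Rank-based case.** Quade's method ranks both volumes over all arms, regresses the 12-month ranks on the preoperative ranks, and runs a one-way ANOVA of the residuals by arm. Simulated power (%), 20,000 trials per setting, bivariate normal volumes, zeros made by censoring:

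| Setting | ANOVA | Kruskal–Wallis | Quade at rho 0 / 0.3 / 0.5 / 0.7 |
|---|---|---|---|
| 14 per arm, 0.9 SD, no zeros | 65 | 61 | 62 / 65 / 74 / 88 |
| 70 patients, 0.9 SD, no zeros | 77 | 74 | 74 / 78 / 85 / 95 |
| 14 per arm, 0.51 SD, no zeros | 24 | 22 | 23 / 25 / 29 / 39 |
| 14 per arm, 0.9 SD, 28% zeros | – | 56 | 57 / 60 / 68 / 83 |
| 14 per arm, 0.9 SD, 49% zeros | – | 45–46 | 46 / 49 / 57 / 69 |

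In the first row the gain over Kruskal–Wallis, before rounding, is 61.5 − 60.7 = 0.8 points at rho 0, 65.4 − 61.0 = 4.4 at 0.3, 74.1 − 61.0 = 13.1 at 0.5, and 88.2 − 60.7 = 27.5 at 0.7. Against raw ANOVA, Quade is 64.8 − 61.5 = 3.3 points lower at rho 0; the worst deficit over all settings run was 4.4 points, also at rho 0.

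**4. Chance imbalance.** An arm mean has standard error SD/√n. The largest gap between any two of four preoperative means exceeds 0.5 SD when the range of four standard normals exceeds 0.5√n. That is 1.871 for n = 14 (probability 0.55) and 2.062 for n = 17 (0.46).

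**The case against.** **A change comparison may already be intended.** The protocol speaks of volume changes, and the SAP's general ANOVA rule could be applied to them. This stands in part: such a test is not excluded, but none is stated. Nor would it fully replace adjustment. With equal variances a change score divides λ by 2(1 − rho), so it beats the unadjusted test only when rho exceeds 0.5. At f = 0.40 and 56 patients it has 51.3, 67.3 and 89.3% power at rho 0.3, 0.5 and 0.7, against 67.3% unadjusted and 71.8, 80.6 and 93.8% with ANCOVA.

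**The benefit is conditional.** This stands in full. Without a known rho the gain may be negligible, zeros shrink it in absolute terms, and at 0.51 SD with 14 per arm power is low either way.

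**Three stronger readings are tempting, and the documents do not support them.** A reader might infer that the SAP never compares preoperative volume between arms; but its time-point comparisons include the preoperative one. A reader might infer that the unadjusted comparison is biased; under randomisation it is not. And a reader might take the 55% and 46% imbalance figures as a defect; they are ordinary chance variation, which the test's type I error already covers, and they matter for precision only if rho is material.

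**Conclusion.** The point holds as one of efficiency. The SAP names no between-arm comparison of the 12-month outcome that uses preoperative volume as a covariate or in a change score, although the protocol measures it and speaks of change. The planned comparison remains valid. With 14 per arm and an assumed 0.9 SD shift, adjustment takes rank-based power from about 61% to between 62% (rho 0) and 88% (rho 0.7). These figures rest on assumed rho, shift and normal volumes; those for 70 patients also assume near-equal arms and no loss over 12 months. It is an optional, cheap improvement, not an error in validity.

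**What to change.** In the SAP's Statistical analysis section:

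- State that the primary between-arm comparison of 12-month volume adjusts for preoperative volume by Quade's rank ANCOVA, chosen because some lesions may heal to 0 mm³.
- Make the six pairwise contrasts by the same method with Bonferroni correction. At 0.05/6 and 14 per arm the simulated familywise error was 0.044–0.051.
- Keep the unadjusted Kruskal–Wallis test as a sensitivity analysis.
- Draw no conclusion between techniques from the within-arm Wilcoxon tests.
- Treat any adjusted difference in mm³ as descriptive. With skewed volumes and up to 49% zeros, nominal 95% bootstrap intervals covered 0.80–0.94 (percentile) and 0.86–0.95 (studentised, checked for one contrast and one direction only).

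Both documents are written in the past tense. If the 12-month data have already been analysed, label the adjusted analysis as added later and report it beside the planned test.

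The cost is SAP wording, a short computation and one degree of freedom, with no new measurement. The downside is up to about 4 points of power against raw ANOVA if the data are normal and rho is near 0. On normal data Quade also has about 1–5 points less power than parametric ANCOVA.

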A 30-gauge side-perforated irrigation needle (Kerr Hawe Sa, Bioggio, Switzerland) was inserted 1 mm shorter than the working length, and the fiber tip was positioned in the center of the access cavity and fixed in this position. Then, 2 ml of 17% EDTA was activated 3 times for 20 s. The same procedure was repeated with 2 ml of 2.5% NaOCl solution by flushing distilled water between each irrigant as described before.

After the final irrigation procedures, the root canals were dried with 25/.06 paper cones (DiaDent, Heungdeok-gu, Korea), and the cold lateral compaction obturation technique with a root canal sealer (Meta Biomed, Cheongju, Güney, Korea) was used to fill all the canals. Permanent restoration was performed directly with composite resin material (Palfique Estelite, Tokuyama Dental Co., Tokyo, Japan).

Follow-up procedures

For routine follow-up, 2D radiographs were taken at 3, 6, and 9 months, as well as via intraoral examinations. Radiographic healing in both 2D and 3D at baseline and at a follow-up of 1 year was assessed by a calibrated evaluator who was blinded to the allocation group. The teeth were assessed for reported symptoms, sensitivity to palpation and percussion, mobility and probing depth. The presence of failure (intraoral swelling or sinus tract) was recorded.

Healing evaluation: lesion area and volume calculation

Twelve months after the root canal treatment, new CBCT images were taken with the same device (Planmeca Promax 3D Classic device (Planmeca Romexis, Helsinki, Finland)) and the same parameters (85 μ m voxel size, 6.3 mA, 90 kV, 8.7 with FOV area 5x5 cm).

3D lesion volume calculation was performed using ITK SNAP (free software under the GNU General Public License developed by the National Institutes of Health, the US National Institute of Biomedical Imaging and Bioenergy needs, the US National Library of Medicine, the Universities of Pennsylvania and North Carolina, and an independent group of developers) by an oral maxillofacial radiologist with 12+ years of experience.

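### The SAP plans only significance tests between arms for lesion volume; it names no between-arm difference or confidence interval, so neither the size of an effect nor what a null result excludes is planned to be shown

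*SAP*

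**What the plan says.** The SAP is a single section, Statistical analysis. Between arms it provides for tests of lesion volume: "To compare lesion volume measurements according to study group at different measurement times, ANOVA and the Kruskal–Wallis test were applied". The pairwise step has a stated purpose: "The post hoc Bonferroni correction was used to determine the group or groups that were significantly different". It identifies which arms differ and does not mention by how much. Within arms, "Wilcoxon signed rank tests were used to compare lesion volume measurements according to different measurement times in the study groups". The remaining analyses concern normality (Shapiro–Wilk), sex (chi-square) and age (Kruskal–Wallis and Spearman).

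The protocol, under Healing evaluation, gives the source of the outcome: "Twelve months after the root canal treatment, new CBCT images were taken with the same device". Volumes come out in mm³ and are set against each patient's preoperative scan. It then says only: "The volume changes were measured, and the long-term outcomes of the procedures were compared". Neither document names a mean or median difference between arms, a ratio, or an interval.

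On size, the protocol's Sample size calculation asks for at least 56 patients, 14 per group. Its section on recruitment and randomization reports 70 randomised to four groups.

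**The concern.** The trial asks whether, and by how much, the irrigation-agitation technique changes periapical healing. A p-value answers neither the "how much" nor, when it is large, the question of what has been excluded. A significant result would arrive without a planned statement of the mm³ gained. A non-significant one would arrive without a planned statement of which differences remain plausible. In a large trial the second gap can be minor, because a null result is then usually a precise one. Here the arms are small, so a null result could be compatible with both no difference and a considerable one, and nothing prespecified would tell the reader which.

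**Working it through.** **Inputs**
- Patients per arm: 14 is the protocol's minimum. With 70 randomised, 70/4 = 17.5, so 17 or 18 per arm if the split is equal. The allocation ratio is not stated, so equality is an assumption. Falling from 70 to 56 would be a loss of 1 − 56/70 = 20%.
- Type 1 error: 0.05 (protocol, Sample size calculation). Sidedness is not stated; two-sided is assumed.
- Number of pairs: 4 × 3/2 = 6 if all are compared. The SAP does not say how many.
- SD of lesion volume: not given, so results are in SD units. Equal SDs and roughly normal volumes are assumed.
- Correlation between baseline and 12-month volume: not given; 0.5 and 0.7 are tried.

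**The plan's own figure.** Neither document gives a precision figure to reproduce. The only related number is the planning effect: "An effect size of 0.51 Cohen d value was found to be sufficient for significance". Its scale has to be settled before it can serve as a yardstick. Read as Cohen d for two means at 95% power, two-sided, it needs 2 × (1.960 + 1.645)² / 0.51² ≈ 100 per arm, not 14. The protocol also says: "The effect size was calculated based on chi-square analysis data between the control group and the laser group". That suggests a chi-square effect size. As w in a 2×2 table, 0.51 would correspond to d = 2 × 0.51 / √(1 − 0.51²) ≈ 1.19. As an ANOVA f with four groups, the spread between extreme arms would be at least 2 × 0.51 = 1.02 SD. The same number could thus stand for 0.51, about 1.02 or about 1.19 SD, so it is not used as a benchmark below.

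**Unadjusted 95% interval, one pair.** Half-width = t(0.975; 2n − 2) × √(2/n).
- n = 14: 2.056 × 0.378 = 0.777 SD
- n = 17: 2.037 × 0.343 = 0.699 SD
- n = 18: 2.032 × 0.333 = 0.677 SD

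**Bonferroni over six pairs, error df pooled over four arms.** Half-width = t(1 − 0.05/12; 4n − 4) × √(2/n).
- n = 14: 2.743 × 0.378 = 1.037 SD
- n = 17: 2.723 × 0.343 = 0.934 SD
- n = 18: 2.718 × 0.333 = 0.906 SD

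The two sets use different df. The choice is minor: at n = 14, pooled df give 0.758 for the single pair, and two-group df give 1.079 for the Bonferroni interval.

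**Baseline-adjusted 95% interval, one pair.** Half-width = t(0.975; 4n − 5) × √(2/n) × √(1 − r²).

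| n per arm | r = 0.5 | r = 0.7 |
|---|---|---|
| 14 | 0.657 | 0.542 |
| 17 | 0.594 | 0.489 |
| 18 | 0.576 | 0.475 |

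**Reading.** If two arms had identical observed means, the unadjusted single-pair interval would still contain true differences of about 0.7 to 0.8 SD in either direction. At the Bonferroni level it would contain differences of about 0.9 to 1.0 SD.

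**The case against.** The strongest reply is that the SAP lists tests without restricting what may be reported. Arm means and mm³ volumes will exist, and an interval can be computed from the same data at any time. No p-value is wrong and no comparison is biased. That is fair, and it limits the point to what is prespecified. It does not remove it: on the Kruskal–Wallis branch the named test gives no difference in mm³, and an estimator chosen after seeing the data is weaker than one fixed beforehand.

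Three stronger readings are tempting and are not supported.
- A reader might infer that a null result will be reported as equal healing, or that a verdict of significant or not is the only output. Neither document says how a non-significant result will be worded, and silence about summaries does not exclude them.
- A reader might infer that a zero difference would still be compatible with more than the planning effect of 0.51. That holds for the unadjusted interval only if 0.51 is a Cohen d. If it is a chi-square w or an ANOVA f, the single-pair intervals would exclude the planning effect. Even as d, the statement fails at 17 per arm with baseline adjustment at r = 0.7 (0.49 SD).
- A reader might infer that the trial is shown to be too small in mm³. Without an SD this cannot be said.

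It can also be objected that 12-month volume is not named as the primary measure, since the protocol speaks of change as well. That is correct, and is one reason to write the estimate down. With baseline as a covariate in a linear model, 12-month volume and change from baseline give the same between-arm difference.

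**Conclusion.** The point holds as an omission in the planned analysis. Between-arm lesion volume is to be tested, with no effect estimate or confidence interval planned in either document. At 14 to 18 per arm the missing intervals would be wide: about 0.68 to 0.78 SD either side for a single unadjusted pair and about 0.91 to 1.04 SD with Bonferroni over six pairs. Baseline adjustment at assumed correlations of 0.5 to 0.7 would give about 0.48 to 0.66 SD for a single pair. These figures rest on equal SDs, roughly normal volumes, a two-sided 0.05 level and, for the upper arm sizes, an equal split of 70. They do not depend on the planning effect. The planned tests remain valid as tests; what is missing is the means to interpret them. The change should be made, but it is not a fatal flaw.

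**What to change.** Keep the tests and add a paragraph to the SAP's Statistical analysis section stating that:
1. for each pairwise comparison reported, the between-arm difference in 12-month lesion volume will be given in mm³, preferably adjusted for the baseline CBCT volume already collected;
2. its confidence interval will be at the same Bonferroni-adjusted level as the test, so that interval and test do not disagree merely because one is corrected and the other is not;
3. one estimator is fixed in advance, for example a mean difference (which combines readily with baseline adjustment), or a Hodges–Lehmann shift if skewed volumes are expected, and is not selected by the Shapiro–Wilk result;
4. a conclusion of similar healing must rest on the interval and not on p > 0.05 alone.

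This needs no new patients or imaging. It costs one extra results table, and null results will visibly look imprecise.
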